2. STUDY OBJECTIVES

2.1. Primary Objective

To estimate the retention rate of RA patients treated with abatacept (regardless of route of administration) over 24 months in routine clinical practice in every participating country and their combinations whenever appropriate, depending on the treatment line (i.e, abatacept as second or further biologics DMARDs or abatacept as first line of biologics DMARDs).

2.2. Secondary Objectives

1. To identify the major determinants (including prior RA treatment experience with biologics and clinical outcomes, such as DAS28, HAQ-DI, CDAI, SDAI, and their derived criteria) of treatment discontinuation of RA patients treated with abatacept in this study.
2. To estimate the distribution of time-to-discontinuation of abatacept therapy for each major determinant of treatment discontinuation, overall, depending on the treatment line

3. To estimate the association of prior RA treatment experience and clinical outcomes during the treatment course with patient reported outcomes (Patient satisfaction, Pain, Patient's Global Assessment).
4. To summarize the treatment experience and outcomes after switching to a biologic or conventional DMARD for patients who discontinue abatacept therapy.

2.3. Exploratory objective

To describe the potential changes in treatment pattern over time in clinical practice by comparing the patients treated with abatacept as second or further biologics DMARDs, enrolled in the study during the period 2008-2010 to patients enrolled in the study during the period 2011-2013 in Europe (Germany, Italy, Austria, The Netherlands, Greece)

To describe the treatment experience and outcomes after switching from abatacept IV to abatacept SC formulation.

[figure not shown]
3. STUDY DESIGN AND EVALUATION

3.1. Study Design

This is a non-interventional, multicenter, prospective, longitudinal survey of RA patients treated with abatacept according to the SmPC in Europe, and the Product Monograph in Canada,.

A total of 2825 patients is expected to be enrolled in the study. The patients will be enrolled prospectively according to participating country regulatory requirements either at initiation of abatacept IV treatment or will have been treated with abatacept IV for maximum 3 months, over a period of a maximum duration of enrolment of 18-24 months for each treatment line of abatacept and for each enrolment period; and at the latest in December 2013. The diagram below (see [Figure 1](#)) describes the different study periods:

Figure 1 Study periods description

* Except in Canada where the Product Monography includes the indication in first line of biologics DMARDs

** In each country the enrolment period duration will be no more than 2 years

*** The data collection period includes the enrolment period and the follow-up period (max 2 years by patient)

In countries where patients can only participate in an observational study once they are already on treatment with the study drug, patients should be included only if baseline data are available and can be collected retrospectively.

Each patient will be followed up for 2 years with a frequency according to routine local clinical practice. Data will be collected retrospectively at baseline (socio-demographics, disease history and characteristics, prior RA treatments such as biologic or conventional DMARDs, and other concomitant medication) and prospectively (clinical and patient-reported outcomes) at baseline and during visits to the treating physicians. Assessment schedules and outcomes will be performed according to routine local clinical practice. It is estimated that patients will be evaluated every 3 months. If available, data at additional visits will also be collected (e.g. at time of drug administration). Patients who discontinue abatacept treatment regardless of the reasons and time of discontinuation will be followed up for 6 months after discontinuation if feasible. Patients who changed abatacept route of administration from IV to SC during the follow up period will be followed up to 2 years. This change is not considered as a discontinuation of treatment, but as a treatment modification. Patient recruitment will be both from outpatient visits and one-day hospitalizations if applicable.

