Baseline assessments for all patients entering the survey are mandatory in order to achieve the objectives. Therefore, in countries where patients can only participate in an observational study once they are already on treatment with the study drug, patients should be included only if baseline data are available and can be collected retrospectively.

Therefore, this study is proposed to collect and analyze data from a sample of prospectively recruited patients to explore the answers and achieve the objectives outlined in this section.

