3.3. Inclusion Criteria

- Male or female subjects of more than 18 years old
- Patients with a diagnosis of established moderate to severe active RA (as per the American College of Rheumatology revised criteria, 1987)³³, who at their physician's discretion are treated with abatacept IV according to the SmPC in Europe and the Product Monograph in Canada (initiating or already on treatment for maximum 3 months) and for whom baseline characteristics are available

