3.5. Criteria for Evaluation

Assessments:

- Baseline (at 1st administration of abatacept IV).- the baseline data can be collected at abatacept IV treatment initiation or retrospectively within maximum 3 months following the first administration:
 - Socio-demographics (age, sex, employment status)
 - Disease history & characteristics
 - Prior RA treatments (biologic and conventional DMARDs, other concomitant medication)
- Prospectively, inclusive of baseline (as defined before):
 - Clinical outcomes: DAS28 and its individual components (SJC, TJC, CRP/ESR), CDAI, SDAI³⁴, HAQ-DI, Physician's global assessment
 - Patient-reported outcomes: Patient Global Assessment, Patient satisfaction, Pain (see Appendix)
 - Abatacept dosage and frequency of administration (IV or SC formulation)
 - Reasons and subsequent RA treatment with conventional/biologic DMARDs if abatacept treatment was discontinued
 - Reason for change in the route of administration of abatacept (from IV to SC)
 - Other concomitant medication for RA (doses, frequency)
 - Adverse Drug Reaction

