4.2. Statistical Analysis plan

All the questionnaire parameters and evaluation criteria (see [section 3.5](#)) will be summarized using descriptive statistics in addition to statistical modelling if needed. Specifically, (1) the sample size, mean, standard deviation, minimum, median, mode, maximum, 95% CI and the number of missing data will be provided for continuous variables; (2) the frequency and percentage by modality, 95% CI and number of missing data will be provided for discrete variables; and (3) the distribution and median of time-to-event data will be analyzed using Kaplan-Meier product limit estimator. The 95 % CIs of the estimates will also be presented. A detailed statistical plan will be developed and approved before database lock.

Data from different countries may be pooled if appropriate, including data from registries.

The analysis will be performed for each participating country. Data from different countries may be pooled if appropriate.

The analysis will be performed separately depending on treatment line of abatacept.

More specifically, the following analysis will be performed:

Primary Analysis:

- The retention rate of RA patients treated with abatacept over 24 months in routine clinical practices will be estimated for each country separately and pooled (if appropriate), depending on treatment line of abatacept
- A change of abatacept route of administration from IV to SC during the follow up period will be not considered as a discontinuation of treatment, but as a treatment modification.

Secondary Analysis:

Information of Participating Centers:

- Descriptive analysis of the participating physicians and assessment of the representativeness with national statistics will be performed. Physicians from the different datasets (respondents accepting participation, respondents refusing participation, non respondents – active and inactive physicians) will be compared to assess the generalizability of the results.

Determinants of Treatment Discontinuation:

- The major determinants of treatment discontinuation of RA patients treated with abatacept in this study will be identified and summarized.
- The retention rate will be estimated for each determinant. The corresponding 95% CI will also be provided.

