4.4.2. Patients

- Patient identification (N° center, N° patient)
- Data collected retrospectively at baseline (first administration of abatacept IV)
 - Socio-demographics
 - Disease history and characteristics
 - Prior RA treatments (biologic and conventional DMARDs, other concomitant medication)
- Data collected prospectively from baseline:
 - Clinical outcomes: DAS28 and its individual components (SJC, TJC, CRP/ESR), HAQ-DI, Physician's global assessment,
 - Patient-reported outcomes: Patient Global Assessment, Patient satisfaction, Pain (see Appendix)
 - Abatacept dosage and frequency of administration (IV and SC formulation)
 - Reasons and subsequent RA treatment with conventional/biologic DMARDs if abatacept treatment was discontinued for 6 months after discontinuation
 - Reason for change in the route of administration of abatacept (from IV to SC)
 - Other concomitant medication for RA
 - Adverse Drug Reactions

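### Late entry of up to 3 months, with no stated time origin and no delayed-entry rule, would bias the 24-month retention rate upward if it is counted from first dose

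*Protocol*

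**What the plan says.** Section 3.1 allows enrolment "either at initiation of abatacept IV treatment or will have been treated with abatacept IV for maximum 3 months". The inclusion criterion in section 3.3 matches: the patient is "initiating or already on treatment for maximum 3 months". A late entrant must therefore still be on abatacept when enrolled. Sections 1.3 and 3.1 add a rule for patients "in countries where patients can only participate in an observational study once they are already on treatment with the study drug": they are included only if baseline data can be recovered retrospectively. These countries are not named.

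Baseline is tied to the first infusion. Section 3.5 says that "the baseline data can be collected at abatacept IV treatment initiation or retrospectively within maximum 3 months following the first administration", and section 4.4.2 likewise equates baseline with first administration.

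The primary analysis in section 4.2 reads: "The retention rate of RA patients treated with abatacept over 24 months in routine clinical practices will be estimated for each country separately and pooled", where pooling is appropriate. Time-to-event data are to be analysed by Kaplan-Meier. Neither this text nor the two-year follow-up in section 3.1 says when the clock starts, and delayed entry is not mentioned. Section 3.6 covers volunteer rheumatologists and non-consecutive patients, but not entry after treatment has begun.

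**The concern.** A patient approached two months after the first dose can be enrolled only if abatacept has not been stopped in those two months. A patient in the same position who had stopped is never seen. If retention is counted from first dose and everyone is placed in the risk set at time zero, the pre-enrolment months of late entrants are event-free by construction, and the estimated curve lies too high from then on.

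The primary result is reported by country, and the share of late entrants depends partly on national regulation. Differences between countries, and any pooled rate, could then partly reflect when patients were enrolled. The direction also favours the conclusion that section 1 sets out to validate, that long-term retention is favourable. Section 3.6.2 accepts departures from consecutive inclusion when their reason is independent of the evaluation criteria. Late entry does not meet that condition, because it selects on still being on drug.

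**Working it through.** **Inputs from the protocol.** Expected 24-month retention is 60% after TNF-inhibitor failure and 65% to 75% in first biologic line (section 4.3.1). Germany has n = 370 with a stated precision of ±5 points (4.3.1). Table 1 gives 1151 patients enrolled in 2008-2010 and 755 expected in first line. The entry window is 0 to 3 months (3.1).

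**Assumptions, not in the protocol.** These are the share f of starters who are approached late, the timing of their entry, and the shape of the stopping hazard.

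**Step 1: the plan's own precision.** The half-width is 1.96 × √[p(1−p)/n].
- Germany: 1.96 × √(0.60 × 0.40/370) = 4.99 points, so the stated ±5 reproduces.
- Pooled first line, n = 755: 3.40 points at 65% and 3.09 at 75%, in line with the stated 3.0 to 3.5.
- Pooled n = 1151 at 60%: 2.83 points.
- Small countries at 60%: 9.6 points at n = 100, 12.4 at n = 60, 19.2 at n = 25.

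**Step 2: formula for the bias.** Let S(t) be true retention from first dose. A patient approached at time u is enrolled only if still on drug, which has probability S(u). Among those enrolled, the rate from first dose without delayed entry is

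naive = S(24) / [(1−f) + f × mean S(u)].

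**Step 3: constant hazard, S(24) = 0.60.** The hazard is −ln(0.60)/24 = 0.02128 per month, so S(3) = 0.938. The mean of S(u) over 0 to 3 months is (1 − 0.93814)/(3 × 0.021284) = 0.969.
- Half approached late, uniformly: 0.60/(0.5 + 0.5 × 0.969) = 61.0%.
- All approached late, uniformly: 0.60/0.969 = 61.9%.
- All entering at month 3: 0.60/0.938 = 64.0%.

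**Step 4: other hazard shapes.** These are Weibull curves with S(24) fixed at 60%. Shape 0.7 means front-loaded stopping (S(3) = 0.888) and shape 1.3 a rising hazard (S(3) = 0.966). Bias in percentage points:

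| Late entry | Shape 0.7 | Shape 1.0 | Shape 1.3 |
|---|---|---|---|
| A quarter, uniform over 0-3 months | +1.0 | +0.5 | +0.2 |
| Half, uniform | +2.1 | +1.0 | +0.4 |
| Half, all at month 3 | +3.6 | +1.9 | +1.0 |
| All, uniform | +4.3 | +1.9 | +0.9 |
| All at month 3 | +7.6 | +4.0 | +2.1 |

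For true retention of 65% to 75% with everyone entering at month 3, the bias is +3.6 to +2.7 at constant hazard and +1.5 to +6.9 over the three shapes.

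Section 1 offers one rough guide to shape: with TNF blockers about 30% stop in year one and about 50% remain at two years. This gives log₂[ln(0.50)/ln(0.70)] = log₂(1.943) = 0.96, close to constant hazard. It concerns other drugs and says nothing direct about the first three months.

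**Step 5: if time zero were enrolment.** For patients all enrolled at month 3, the rate 24 months later is S(27)/S(3): 64.7% (shape 0.7), 60.0% (1.0) or 57.1% (1.3). The direction is then not assured.

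**Step 6: does delayed entry repair it?** In a simulation of 400,000 starters at constant hazard, with half approached uniformly over 0 to 3 months, the naive rate was 60.9%. Kaplan-Meier with each patient joining the risk set at enrolment gave 59.95%, against a true 60%.

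**The case against.** A reader might infer three stronger statements, and the documents support none of them.

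- **That retention is counted from first administration.** The protocol ties baseline data to the first dose but gives no time origin for the primary endpoint. First dose is the natural reading, but it is an inference, and Step 5 shows that the upward direction depends on it.
- **That early stoppers are never enrolled.** Section 3.2.1 tells sites to include each subsequent patient who is going to receive abatacept, section 3.6.2 asks for consecutive patients, and section 3.1 allows entry at initiation. Early stops among patients enrolled at initiation are recorded. Only those among patients approached late are lost.
- **That the bias swamps the stated precision.** At 60% retention it exceeds 5 points in only one scenario, where everyone enters at month 3 and stopping is front-loaded. The ±5 applies to Germany alone, and nothing says that Germany restricts entry to treated patients. For most countries in Table 1 the half-width is much larger than any plausible bias.

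It is also fair to say that section 4.2 defers detail to a separate analysis plan, which could handle left truncation, and that the 3-month cap bounds the effect. Both points reduce the severity. They do not remove the concern, because the entry rule, the baseline definition, the missing time origin and the bias discussion are all in the protocol.

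**Conclusion.** The concern holds in conditional form. The protocol mixes new starters with patients selected for still being on drug, does not fix time zero, and does not recognise the left truncation that follows. If retention is counted from first dose without delayed entry, the 24-month rate is biased upward, and more so where entry is possible only after treatment has begun.

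The size cannot be determined from the documents. At a true 60% and constant hazard it is roughly +1 to +4 points, and over all shapes and late shares tried it is +0.2 to +7.6. It matters most for pooled estimates, because pooling shrinks the half-width to about 3 points but does not shrink the bias. With half approached late at constant hazard, +1.0 is about a third of the 2.83-point half-width at n = 1151. For small countries the bias lies inside sampling error.

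**What to change.** - In section 4.2, state first administration as time zero. In the Kaplan-Meier and Cox analyses, let each patient join the risk set at the enrolment date.
- Confirm that both the first-dose date and the enrolment date are recorded. The patient data listed in section 4.4.2 do not name an enrolment date.
- Report the share of late entrants by country, and add a sensitivity estimate restricted to patients enrolled at initiation.
- Where almost nobody is at risk in the first months, report retention conditional on being on abatacept at month 3, labelled as a different quantity that is not directly comparable with the other countries' rates.
- Name the bias, and its likely direction, in section 3.6.

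The cost is wording and, if it is missing, one date field. Intervals will be somewhat wider, the estimate may be unstable where few patients are at risk in months 0 to 3, and the reported retention will probably be slightly lower.

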3.2. Study Population

3.2.1. Sampling Plan

The study will be proposed to rheumatologists at either hospital or private practice. Treatment should be initiated and supervised by specialist physicians experienced in the diagnosis and treatment of rheumatoid arthritis.

A two-stage recruitment strategy will be implemented, with patient recruitment following a center selection procedure.

Selection and recruitment of a national sample of centers:

A general list of rheumatologists (centers) will be compiled (BMS data on file) in each country:

- Approximately 700-1400 in Germany
- Approximately 200 in Austria
- Approximately 242 in Belgium
- Approximately 52 in Czech Republic
- Approximately 300 in Greece
- Approximately 880 in Italy
- Approximately 230 in the Netherlands
- Approximately 55 in Ireland
- Approximately 120 in Denmark
- Approximately 231 in Canada
- Approximately 700 in France
- Approximately 800 in Spain
- Approximately 70 in Switzerland

A letter will be sent to centers with an overall description of the study and an enquiry on potential interest to participate. Rheumatologists will be invited to participate in the study by a letter signed and mailed by Bristol-Myers Squibb. It is assumed that a minimum response rate of 10-20% will be obtained (as not all centers on the general list of centers are treating patients with biologics). To estimate the actual response rate, a small number of invitation letters will be sent to a subset of rheumatologists first. The number of additional letters to be sent out in order to recruit the required number of rheumatologists will be determined accordingly. Rheumatologists will be stratified by country. Obtained responses, either positive or negative, will be tracked and recorded. If the targeted number of rheumatologists is not reached after mailing, non-responding rheumatologists will be contacted by phone, within each stratum, until the targeted number is reached.

Rheumatologists will be requested to provide a brief description to characterize their center: by treatment setting (private rheumatologists or hospital, or institutions), geography (large city or town, $\geq 100,000$ inhabitants, vs. small town), type of institution (academic vs. non academic), number of physicians providing care to RA patients, and volume of patients. Site eligibility will be determined based on site willingness to participate.

Selection of patient cohort:

Site initiation will take place for each rheumatologist agreeing to participate. When the site is initiated, the participating rheumatologist will have to collect data and include each subsequent RA patient, who at the rheumatologist's discretion is to be treated with abatacept IV, up to a maximum of 10 patients (for each treatment line of abatacept) over an accrual period of no more

than 2 years for each treatment line of abatacept and for each enrolment period, up to December 2013. Actual recruitment will depend on the volume of patients managed at each center.

To ensure that the patient sample is representative for the RA population, the targeted population of physicians should be representative for the rheumatologists involved in the treatment of RA patients.

The data of the rheumatologist sample will be closely examined by comparing the sample to the local rheumatologist population (BMS data on file) with respect to the characteristics detailed above (see Selection and recruitment of a national sample of centers) to determine the degree to which generalizability of study samples (both rheumatologists and patients) may be established. The findings as well as the assessment of the potential sources/direction of biases introduced by non-random samples will be reported. The demographics of study respondents vs. non respondents will be also assessed.

National registry:

Participation of Rheumatologists in the study as defined before is based on a voluntary basis. If a national registry is already implemented or planned in the participating country, one can anticipate that a large part of the invited rheumatologists will refuse to participate to the study to avoid collecting the same data twice. In that case this sampling process should not be applied. This situation was identified in Czech Republic and in Belgium. Therefore in these countries data will be extracted from the registries to be integrated in the statistical analysis of the IM101-151 study.

The major part of rheumatologists prescribing biologics are participating to the national registry and we assume that they are representative for the rheumatologists treating RA patients. A sample of Rheumatologists involved in the registry and who accepted to participate in IM101-151 study will collect specific data of the first subsequent patients fulfilling the inclusion and exclusion criteria of this study (see sections 3.3. 3.4) .

3.3. Inclusion Criteria

- Male or female subjects of more than 18 years old
- Patients with a diagnosis of established moderate to severe active RA (as per the American College of Rheumatology revised criteria, 1987)³³, who at their physician's discretion are treated with abatacept IV according to the SmPC in Europe and the Product Monograph in Canada (initiating or already on treatment for maximum 3 months) and for whom baseline characteristics are available

3.4. Exclusion Criteria

- Patients who are currently included in any interventional clinical trial in RA.

